11.2. Assessment of the incision

All subjects will have an incision healing check visit two weeks after both implantation and explantation. Any adverse symptoms (site pain, site warmth, site swelling, fever, etc.) will be summarized by visit and severity (mild, moderate, or severe).

11.3. Vital signs

Vital signs (weight, height, body mass index, temperature, pulse rate, respiratory rate, and blood pressure) are collected according to the schedule in Exhibit 1. All available vital signs data will be presented in a by-subject listing.

12. References

13. Appendix

13.1. Partial dates

Partial dates in the medication and adverse events data will be imputed. Completely missing dates will not be imputed. Partial start dates will be imputed as follows:

- Dates with only missing day will be imputed to the first of the month. However, if the month and year of the partial date are the same as the month and year of the device implantation date, the partial start date will be imputed to the device implantation date.
- Dates with missing day and month will be imputed to January 1st of the given year. However, if the year of the partial date is the same as the year of the device implantation date, the partial start date will be imputed to the device implantation date.

Partial end dates will be imputed as follows:

- Dates with only missing day will be imputed to the end of the month.
- Dates with missing day and month will be imputed to December 31st of the given year.

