5.3. OAB drug-free

The OAB drug-free population will include all subjects in the mITT population who took no medication for OAB during the study period.

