8.3. Demographics and baseline characteristics

Demographic and baseline characteristics will be summarized by age, gender, ethnicity, race, current smoker, and any abnormal findings from a complete physical exam.

Age in years will be calculated as the integer portion of the following:

$$[(\text{Date of enrollment} - \text{Date of birth}) + 1] / 365.25$$

Percentages will be calculated relative to the number of subjects enrolled.

OAB history will be presented. It will include duration of OAB and success of prior treatments (PTNS therapy, TENS therapy, OAB medications, and Botox). Success will be categorized as “yes”, “no”, or “short-term/partial response.”

Medical history will be coded using the Medical Dictionary for Regulatory Activities (MedDRA) and will be summarized by system organ class (SOC) and preferred term (PT).

Prior medications, defined as medications started prior to device implantation, will be presented by their drug generic names, as reported on the prior medication case report form (CRF). The number and percentage of subjects who took at least one drug within each generic type will be presented. Prior medications will be presented separately for OAB and non-OAB medications.

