10.4.2. Additional OAB medications

Medications for OAB are not allowed until the primary effectiveness endpoint is reached at 48 weeks post-activation, unless judged medically necessary. Any subjects who have taken OAB medications will be included in the primary effectiveness outcome variable analysis. OAB medication use will be reported alongside the primary analysis. The timing of OAB medications will be displayed, including duration of treatment, start and end dates, and dosage.

The following additional sensitivity analyses may be performed.

- For the primary effectiveness outcome variable at week 48, data for subjects who have taken OAB medications while on study will be considered missing and imputed assuming they had not taken any OAB medication.
- For weeks 4, 8, 12, 24, 36, and 48, 2 different sets of analyses will be performed.
 - *While on OAB medication.* Subjects will be imputed as non-responders while they are taking OAB medication.
 - *Any OAB medication.* A very conservative set of analyses will consider a subject a non-responder at every visit after she starts OAB medication.

For example, no matter what subjects write on their diaries, the “while on OAB medication” analyses will consider subjects as non-responders from week 12 through week 36 if they take OAB medication at week 12 and stop that medication at week 36. The “any OAB medication” analyses will consider such subjects non-responders from week 12 through week 48.

11. Safety summaries

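### SAP 13.1 can date a pre-study OAB drug to the implant day, even after its own known stop date, and so misclassify it as concomitant

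*SAP*

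**What the plan says.** SAP 13.1 covers two kinds of data at once: "Partial dates in the medication and adverse events data will be imputed". For starts, "Dates with missing day and month will be imputed to January 1st of the given year"; but "if the year of the partial date is the same as the year of the device implantation date", the start becomes the implantation date instead. A start that lacks only the day goes to the first of its month, or to the implantation date if month and year match. For ends, "Dates with missing day and month will be imputed to December 31st of the given year", and a missing day becomes the last day of the month. No clause compares an imputed start with the stop date, and none refers to the washout or to the form on which the drug was recorded.

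Other sections use these dates or could use them:

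- SAP 8.3: "Prior medications, defined as medications started prior to device implantation", taken from a prior-medication CRF.
- SAP 8.5: a therapy is concomitant if it began on or after implantation, taken from a concomitant-medication CRF. The section adds that a therapy taken before implantation is not concomitant, and also that a drug listed at screening and later stopped is counted as concomitant.
- SAP 5.3: the OAB drug-free set is the mITT subjects who "took no medication for OAB during the study period". The per-protocol set (SAP 5.4) is nested in it.
- SAP 10.4.2: OAB drug use, with start, end and duration, is shown beside the primary result. An optional analysis "will consider a subject a non-responder at every visit after she starts OAB medication".

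**The concern.** For adverse events, moving an unclear start to the implant date is conservative: the event is counted as treatment-emergent. The same move does not carry over to drugs. A drug stopped before the study is pushed forward onto the study, and the imputed record can contradict a stop date that the site knew.

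Inclusion criterion 8 requires intolerance of, or inadequate response to, an earlier therapy. OAB drugs are two of the four routes, so histories of such drugs will be present. If the analysis sets are built from imputed dates, a subject who took no OAB drug on study could be removed from the drug-free and per-protocol sets, or scored as a non-responder in the *any OAB medication* analysis. SAP 10.4 says the efficacy analyses will be repeated in both sets, so those repeats are not optional.

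**Working it through.** **The rule on test records.** The documents give no figure for this point, so the check applies the SAP 13.1 rules to six records, with an assumed implant date of 15 October 2018.

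- Imputed start, month unknown = implant date if the start year is the implant year; otherwise 1 January.
- Imputed end = 31 December if the month is unknown; month end if only the day is unknown.

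| Record | Start recorded | Stop recorded | Imputed interval | Result |
|---|---|---|---|---|
| A | 2018 | 10 Sep 2018 | 15 Oct 2018 to 10 Sep 2018 | start after known stop; concomitant by start date |
| B | 2018 | 2018 | 15 Oct 2018 to 31 Dec 2018 | false on-study use |
| C | 2017 | 10 Sep 2018 | 1 Jan 2017 to 10 Sep 2018 | correctly prior |
| D | Mar 2018 | 10 Sep 2018 | 1 Mar 2018 to 10 Sep 2018 | correctly prior |
| E | 2017 | 2018 | 1 Jan 2017 to 31 Dec 2018 | prior by start, but false use after implant |
| F | 2018 | Sep 2018 | 15 Oct 2018 to 30 Sep 2018 | start after stop month |

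In A the start falls 35 days after the stop (20 days left in September + 15). In B and E the false use runs from implant for 16 + 30 + 31 = 77 days. Activation at 28 days is 12 November, week 4 is 10 December and week 8 is 7 January 2019, so the interval covers activation and week 4.

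**Who can be caught by the start rule.** Washout is 14 days before baseline (inclusion criterion 7), and baseline is at least 7 days before implant (protocol 3-4-2). In an eligible subject a pre-study drug therefore stops at least 14 + 7 = 21 days before implant. The days in the implant year on which it could have started are:

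- implant 1 Aug 2018: latest stop 11 Jul, 191 days;
- implant 15 Oct 2018: latest stop 24 Sep, 266 days;
- implant 15 Jan 2019: latest stop 25 Dec 2018, 0 days;
- implant 1 Apr 2019: latest stop 11 Mar, 69 days.

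For the missing-day rule, start and stop must both lie in the implant month, so implant must fall on day 1 + 21 = 22 or later. That case is almost empty.

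**Possible effect on the optional *any OAB medication* analysis.** Inputs: N = 120 and the 40% goal (SAP 6). The exact lower bound is the 2.5% quantile of Beta(r, N − r + 1). As a check, 60/120 gives 0.407, which agrees with the 0.41 in SAP Table 2; 59/120 gives 0.399. Each misclassified subject who would otherwise respond costs 1/120 = 0.83 points. The number affected is unknown, so a range is assumed from 66/120 responders:

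| Responders misclassified | Responders left | Lower bound |
|---|---|---|
| 0 | 66 | 0.457 |
| 1 | 65 | 0.448 |
| 3 | 63 | 0.432 |
| 6 | 60 | 0.407 |
| 8 | 58 | 0.391 |

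The primary analysis does not change, because SAP 10.4.2 keeps every OAB-drug user in it.

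**The case against.** The strongest reply is that nothing in the plan derives on-study OAB use from imputed dates. The drug-free set is defined by drug taken, not by a start date. Protocol 3-4-12 has every subject asked about OAB drugs at each follow-up visit, with a yes recorded on the visit CRF and a concomitant-medication CRF. Prior drugs have their own CRF. SAP 8.5 says that a therapy taken before implantation is not concomitant. Protocol 3-9-6 mentions partial-date imputation only for safety variables. Criterion 7 makes sites confirm the washout, so a recent stop known only to the year should be uncommon. Criterion 8 can also be met through onabotulinumtoxinA or PTNS. Finally, the OAB-medication analyses are optional, and misclassification in the *any OAB medication* version can only count against the device.

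Much of this stands. A reader might infer that subjects who took no OAB drug on study will in fact be classed as users. The documents do not support that: they leave open whether imputed dates or direct evidence decide. A reader might also infer that any unknown start month triggers the problem. It does not: record C, with an earlier start year and a known stop, is handled correctly.

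The safeguards still do not remove the gap. SAP 13.1 and the definitions in 8.3 and 8.5 give opposite answers for record A, and no text says which governs. The separate CRFs do not settle it either, because 8.5 also counts a screening-listed drug that is later stopped as concomitant, which could catch washed-out drugs. The study period in SAP 5.3 is not defined in days.

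**Conclusion.** The point holds as a gap in the date rule that can misclassify some pre-study OAB drugs. It arises in two ways: a year-only start in the implant year, which can fall after a known stop, and a year-only stop in the implant year, which creates false use up to 31 December whatever the start year. A drug with an earlier start year and a known pre-implant stop is not affected, and the primary result cannot change.

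The certain exposure is the prior and concomitant medication tables and the OAB-drug display beside the primary result. The drug-free and per-protocol sets and the optional sensitivity analyses are exposed only if they are programmed from imputed dates. The number of records is not given and may be small. The lower bounds above are illustrations under assumed counts, and the 40% goal is not a success criterion for those analyses. A rule that can start a drug after its known stop is still worth correcting at any frequency.

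**What to change.** Amend SAP 13.1, for medications only:

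1. An imputed start may not be later than the known stop date, or than the last day of the known stop month. This repairs records A and F.
2. Where the prior-medication CRF or washout record shows that the drug was stopped before baseline, cap a partial stop at the baseline visit, cap the imputed start at that stop, and class the drug as prior. This is needed for B and E, where the stop is itself imputed and item 1 alone does nothing.
3. A drug recorded as continuing or restarted on or after implantation still counts as on-study use, whichever CRF holds it. Without this, item 2 could hide real use; SAP 2.5 itself gives incomplete washout as an example of an eligibility violation.
4. For the drug-free and per-protocol sets and the OAB-medication analyses, define on-study OAB use by evidence of use on or after implantation (visit question, concomitant-medication CRF, stop date), not by an imputed start alone. Reconcile this with the SAP 8.5 sentence on screening-listed drugs later stopped.

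Keep the implant-date default for adverse events and for concomitant-CRF records with no evidence of earlier use.

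The cost is SAP wording and a few lines of code, with no new data. Under SAP 7.3 the change belongs in a revised plan before database lock; made later, it would be labelled exploratory.

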13.2. Missing data for primary efficacy outcome

The primary efficacy analysis is based on the proportion of responders at 48 weeks post-activation. Subjects for whom 48 week post-activation data are unavailable but the device is known not to have been explanted or subjects who have been explanted for an MRI will have the primary endpoint data imputed. The missing data for the primary effectiveness outcome variable will be assumed missing at random and will be handled with multiple imputation.

The multiple imputation procedure will use fully conditional specification (FCS) and create 100 imputed datasets. The type of model used for FCS will depend on the variable with missing outcome data. Continuous variables will use regression with predictive mean matching; ordinal and nominal classification variables will use response logistic regression. All variables will be assessed for collinearity before inclusion in the multiple imputation model. Table 3 lists the variables with descriptions that will be used in the model.

The imputation will follow the sample SAS version 9.4 code provided in Exhibit 2. The SAS code may be modified slightly as needed according to software updates and compatibility with actual data. For example, the order of the variables in the VAR statement of the PROC MI procedure will be adjusted to approach monotone missingness. The variables are imputed sequentially in the order specified in the VAR statement with FCS.

The 100 complete datasets created by multiple imputation will be analyzed separately by imputation. The SAS PROC MIANALYZE procedure will be used to combine results from the 100 analyses.

Table 3. Variables in the multiple imputation model

Type	Variable	Description
Binary	SEX	Sex
Continuous	AGE	Age
Continuous	BMI	BMI at baseline
Binary	TENSR	Response to the TENS protocol
Continuous	BASE_OABQ	Baseline OABq total score
Continuous	OABQ4	Week 4 OABq total score
Continuous	OABQ8	Week 8 OABq total score
Continuous	OABQ12	Week 12 OABq total score
Continuous	OABQ24	Week 24 OABq total score
Continuous	OABQ36	Week 36 OABq total score
Continuous	OABQ48	Week 48 OABq total score
Ordinal	PGI4	Week 4 PGI-I questionnaire score
Ordinal	PGI8	Week 8 PGI-I questionnaire score
Ordinal	PGI12	Week 12 PGI-I questionnaire score
Ordinal	PGI24	Week 24 PGI-I questionnaire score
Ordinal	PGI36	Week 36 PGI-I questionnaire score
Ordinal	PGI48	Week 48 PGI-I questionnaire score
Continuous	BASE_VOID	Baseline urinary voids averaged per 24 hours on a 3-day voiding diary
Continuous	VOID4	Week 4 urinary voids averaged per 24 hours on a 3-day voiding diary
Continuous	VOID8	Week 8 urinary voids averaged per 24 hours on a 3-day voiding diary
Continuous	VOID12	Week 12 urinary voids averaged per 24 hours on a 3-day voiding diary
Continuous	VOID24	Week 24 urinary voids averaged per 24 hours on a 3-day voiding diary
Continuous	VOID36	Week 36 urinary voids averaged per 24 hours on a 3-day voiding diary
Continuous	VOID48	Week 48 urinary voids averaged per 24 hours on a 3-day voiding diary
Continuous	BASE_UUI	Baseline UUI episodes averaged per 24 hours on a 3-day voiding diary
Continuous	UUI4	Week 4 UUI episodes averaged per 24 hours on a 3-day voiding diary
Continuous	UUI8	Week 8 UUI episodes averaged per 24 hours on a 3-day voiding diary
Continuous	UUI12	Week 12 UUI episodes averaged per 24 hours on a 3-day voiding diary
Continuous	UUI24	Week 24 UUI episodes averaged per 24 hours on a 3-day voiding diary
Continuous	UUI36	Week 36 UUI episodes averaged per 24 hours on a 3-day voiding diary
Continuous	UUI48	Week 48 UUI episodes averaged per 24 hours on a 3-day voiding diary

Exhibit 2. Sample SAS code for multiple imputation for primary analysis

```
**** Impute missing values to create 100 imputed datasets;
proc mi data=OBSERVE nimpute=100 seed=938279 out=OBSERVE2;
  class SEX TENSr PGI4 PGI8 PGI12 PGI24 PGI36 PGI48;
  var SEX TENSr PGI4 PGI8 PGI12 PGI24 PGI36 PGI48 BMI AGE BASE_UUI UUI4 UUI8 UUI12
      UUI24 UUI36 UUI48 BASE_VOID VOID4 VOID8 VOID12 VOID24 VOID36 VOID48 BASE_OABQ
      OABQ4 OABQ8 OABQ12 OABQ24 OABQ36 OABQ48;
  fcs regpmm (BASE_UUI UUI4 UUI8 UUI12 UUI24 UUI36 UUI48 BASE_VOID VOID4 VOID8
      VOID12 VOID24 VOID36 VOID48 BASE_OABQ OABQ4 OABQ8 OABQ12 OABQ24 OABQ36
      OABQ48 / details) ;
  fcs logistic (SEX TENSr PGI4 PGI8 PGI12 PGI24 PGI36 PGI48 / link=logit
      likelihood=augment);
run;
```

E:\Proj\Valencia OAB\2. SAP\Valencia OAB SAP_v.003.docx\SB
